b. Population

- 1. Adults (n=44) with moderate to severe OSA.
- 2. Potential study participants will be recruited by means of flyers posted at the College of Dentistry, Dallas A.W.A.K.E. office (support group for sleep apnea patients) and Dallas area sleep clinics. Online postings at clinicaltrials.gov and the College web site. Also post flyers at (1) regional hospitals and clinics, (2) city and county offices/stations (such as the Dallas Fire Department), (3) DART and other transportation offices and (4) Facebook, Twitter and similar site, (5) local newspapers and magazines, (6) local radio stations. The content of the advertisements on venues (5) and (6) will be the same as the approved flyers. Written permission will be sought from all sites at which flyers are to be posted. Data analyst and subjects will be blinded to treatment device type (i. e. sequence of use of the two OAs) and subject's identity will be coded.
- 3. Controls and Controlling Confounders: Subjects serve as their own controls; their baseline polysomnography (PSG) or Home Sleep Test (HST), untreated values (from full or split night PSGs) will serve as their control values for evaluating treatment effects with each of the two OAs. The focus of the trial is on comparing OA appliance efficacy in reducing the RDI (AHI); the presentation, fitting, monitoring and adjustment of the two OAs will be the same for both arms of the study. For the operators, there will be concealed allocation of assignment of subjects to treatment.
- 4. Performance Site: Texas A&M College of Dentistry, [name]. Seventh floor room 725, two operatory clinic.

c. Inclusion criteria

OSA diagnosed adults, at least 18 years old, who have been recently diagnosed by polysomnography (PSG) or polygraphy home sleep test (HST) in the previous year and are currently being treated with continuous positive airway pressure (CPAP) having an AHI > 15 events/hour of sleep; two or more OSA symptoms (snoring, witnessed apnea or daytime hypersomnolence complaint); at least 8 teeth per arch to support either OA device; Mallampati score from I to III; Palatine tonsils – grade 0, 1, or 2; Central and mixed apnea index < 5 events /hour. Consent to study's timeline; willingness to wear home sleep test apparatus for at least 4 nights and to wear an oral appliance every night for 8 weeks; willingness to pick up and return home sleep test kits as needed.

d. Exclusion criteria

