Cardiac & pulmonary disease (e.g., congestive heart failure, severe arrhythmias, COPD); central sleep apnea; comorbidities of other sleep disorders other than OSA; no active TMD or jaw muscle pain, morphological airway abnormalities, BMI ≥35; pre-existing difficulty swallowing; throat or neck related health issues; endocrine dysfunction; severe psychiatric disorders; intellectually disabled; previous OA therapy; previous ENT surgery; restrictions in jaw opening; pregnant / breast feeding or intent to become pregnant during the study; inability to provide informed consent and apply the HST recorders.

e. Table 4: Variables of Interest: Primary, Secondary and Exploratory

Prima	ry	Secondary	Exploratory
with f of-tre secon treatn OA; T	art-of-treatment irst OA; T ₂ -end-atment with d OA; T ₃ -start-of-nent with first f ₄ -end-of-nent with second	T ₁₋₄ Snore count; OA compliance; Mean disease alleviation; Sleep Quality T _{0, 2, 4} Epworth Sleepiness Scale score; Short Form-36 score Thornton snoring scale Sleep observer scale Symptom alleviation Changes in occlusion as measured by shim stock, tested before and after	T ₄ OA device preference and perceptions of comfort; Development of a cost effective titration protocol with maximal patient convenience.

Mean disease alleviation is a composite measure of the reduction in RDI and OA compliance. RDI, respiratory disturbance index equals the number of respiratory events per hour of recorded time; $T_{1,4}$, time points 1-4

- f. Data collection techniques to be used during sleep
 - 1. OA compliance
 - i. This variable is determined by the number of hours that the OA device is worn per hour of sleep per night using Braebon monitors (integrated chips; Kanata, Ontario, Canada)
 - 2. Respiratory measures (Figure 3)
 - Braebon polygraphy (PG) recorder for home sleep testing: airflow, respiratory effort, electrocardiogram (ECG), pulse oximetry, anterior tibialis electromyography, body position, and snore sound.

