Treatment devices: TAP 1 (Airway Management Inc., Dallas, TX; MT type OA device) and SomnoDent Flex (SomnoMed, Plano, TX; BT type OA). Both OA devices will be used per manufacturers' recommendations. To insure comparability, both devices have a custom thermal acrylic liner insuring a very accurate fit. Each subject will also be custom fitted with a mandibular positioner ("AM Aligner" or "Morning Positioner") to use for up to 20 minutes after awakening in the morning; this will assist in returning the subject to his/her normal occlusion.

Appliance Acclimation: Both appliances will be adjusted / titrated to the patient's maximal comfortable protrusive position by patient in the wake state. The starting position will be determined by the patient at a comfortable position but not less than 60% as determined by the Pro Gauge. "Comfortable" is defined as the advanced mandibular position that permits the subject to sleep for ≥ 5 hours per night for at least 6 nights of the week. Subjects will use diaries to record appliance settings and hours of sleep on each sleep recorded or non-recorded night. Two follow-up nights (post T_1) of SleepImage recordings only will be made to track sleep quality and OA position, if further mandibular adjustments are necessary as determined by the T_1 & T_3 HST and SleepImage results.

Course of Treatment: Subjects will be randomly assigned to either the MT- or BT-first OA device as treatment for OSA. Each subject will use the first OA for 4 weeks followed by – 1 week washout period that includes using nightly their prescribed CPAP and daytime use of a mandibular positioner (for up to 20 minutes) – then another 4 weeks of active treatment with the second OA.

h. Power Analysis and Sample Size

At least 38 subjects with OSA are needed to yield a power of 0.90 with alpha = .05 and an expected Effect Size of at least a 10 point difference in the post-treatment mean RDI scores between MT vs. BT devices.Recruitment will be extended to n=44 to accommodate an estimated 20% drop-out rate. The projected numbers are based on Wilcoxon signed-rank test where the expected difference between-treatments (cross-over design) is expected to be at least 10 point difference in RDI scores.

i. Statistical analyses

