b. After meeting the study's inclusion and exclusion criteria through telephone screening, study subjects will receive detailed information about the study from the Study Coordinator during their first appointment. The first appointment to the study center will include obtaining a copy of the patient's PSG/CPAP study reports and medical history, completion of the study's intake assessment, signing the informed consent form and obtaining impressions and protrusive bite. In the absence of a current PSG, subjects will be sent home with a HST to collect comparable baseline information. Both oral appliances will be constructed prior to the second appointment. The subjects will be randomized to an OA device at second appointment (this will allow any questions by the lab of the dentist to improve the device). During the second appointment, subjects will be examined and fitted by the dentist with both OAs. Subjects will be then scheduled within 4-weeks for the first HST with simultaneous SI recording for determination of the RDI and sleep quality criteria. Recordings will occur x1/subject at T₁ (first night in week-1 with first OA), T₂ (after four weeks using first OA), a washout period of 1 week using a mandible repositioner daily and CPAP nightly, T₃ (first night of week-6 with second OA) and T₄ (after four weeks using second OA). (Figure 1, below; Table 1)

c. Table 5: Protocol for determining subject candidacy:

EVALUATION	PURPOSE	PROCEDURE/RATIONALE
Recruitment / Orientation	Provide information about the study.	Provide the subject with information regarding the OA devices, the clinical study and an information brochure.
Medical Background Information	Gather information regarding the subject's medical background to determine candidacy, and recent sleep study evaluations.	Standard medical case history and physical with emphasis on OSA to include the Medical/Surgical History as part of the Case Report. Conducted individually by the team/Study Coordinator and discussed collectively to ensure that the subject has realistic expectations for the study.
Craniofacial & Oral Testing	Verify subject qualification with a craniofacial / oral exam.	Clinical assessment is performed to examine the upper airway and oropharynx to determine the subject qualification for using OA therapy.
Informed Consent	Obtain informed consent.	Informed consent will be obtained by providing information related to the time commitments of the trial, risks and contraindications.

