Each participants involvement in the study while at home is as follows: On each of 4 nights over the course of 9 weeks the subject will put on the HST and SI prior to bedtime, and remove them upon awakening. The two systems include attaching sensors to various parts of the face, chest and abdomen. Adhesive pads and surgical tape are used to hold these devices and wires in place. Placement may take up to 20 minutes, and removal, about 5 minutes. The coordinator will demonstrate how to apply the sensor properly to insure valid recordings. Minor discomfort may be experienced when pulling off the tape. If a first night recording is faulty, a subject may be asked to do a second night recording: subjects will not be asked to record for more than 8 nights in total. Subjects will wear an OA every night for 4 weeks, no OA for the 1-week washout period, and an OA (the alternate device) for each night for another 4 weeks. They will put on the OAs prior to bed and remove them upon awakening. The OA will contain a computer chip that will also record the actual amount of time that the OA is worn each night. Subjects use their CPAP devices each night of the washout period as prescribed by their physicians. Some discomfort and/or tendeness in the temportomandibular joint (jaw joint or TMJ) and jaw muscles may be experienced during and after OA use. Also some minor tooth movement and discomfort may be experienced. In addition to their OAs, each subject will be given a mandibular repostioner, a small custom bite splint to be worn for two minutes after removing the OA upon awakening. Use of the mandibular repostioner will minimize or eliminate the aforementioned discomforts and tooth movement. All of this clinical care, potential discomforts and tooth movements will be carefully monitored and managed by the dentists on the research team.

How long will the participants be engaged in the research (length of time, e.g., 15 minutes, 45 minutes on Day 1, 60 minutes on Day 2, etc.)?

Visit 1: 120 minutes; Visit 2: 60 minutes; Visits 3-9: 15 minutes each. Total in office commitment: Approximately 5 hours. For the home sleep tests, approximately 30 minutes for at least 4 nights(but no more than 8 nights), for a total of at least 2 hours (but no more than 4 hours)

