- How will the device be used? Each of the test custom-fitted OAs will be worn each night during sleep for a 4-week period with a 1-week washout period between test OAs. The subject is expected to wear their prescribed CPAP during the washout period. The HST recorders to evaluate sleep quality with OA use will be obtained by study subjects for each of the two OA testing periods on the first and last day of each 4-week period. A total of 4 sleep recordings/subject is expected over the 9-week study period.
- How will the device be destroyed and disposed? The HST recorders are reusable/non-disposable items, so they will not be destroyed.
- Alternatives available to patients: No alternative treatment options are directly part of this study.
 If a prospective subject decides that either oral appliance therapy is not suitable for him/her, the
 alternative is to continue to use his/her prescribed CPAP therapy.

26.0

Before you Submit

26.1 Please note the following.

The following checklist is a guide for researchers regarding supporting documents that must be considered for and/or uploaded with this application for review and approval before use.

- Informed Consent Document
- Information Sheet
- Waiver of HIPAA Authorization
- Parental Permission Form/Minor Assent Form
- Recruitment materials (i.e. flyers, emails, advertisements, telephone scripts, social media posts)
- Site Authorization Letter (for study conduct and/or access to administrative records)
- Survey/Questionnaire/Data Collection/Abstraction Forms
- Grant Applications (cover to cover), required if funded or grant submitted
- Instructions
- Protocol Investigator's Brochure (for clinical trials only)
- Case report form (for clinical trials only)
- Device Manual (if using an approved or investigational device)
- Thesis/dissertation proposal
- Waiver of parental permission/minor assent form
- Letter of cultural evaluation for international research (link to SOP)
- IRB approvals from collaborating institutions
- Any other documents related to the research
- CVs for all investigators when proposed activities are more than minimal risk
- CITI training for all personnel

Investigators assume the following responsibilities:

- Continuing Review: The study must be renewed by the expiration date in order to continue with
 the research. A Continuing Review application along with required documents must be submitted
 by the continuing review deadline. Failure to do so may result in processing delays, study

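### OA compliance and mean disease alleviation are listed at T1–T4, which are single recording nights, with no whole-period window and no composite formula

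*Combined protocol and SAP*

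**What the plan says.** Section VII.e, Table 4 (Variables of Interest), lists these secondary variables under T1–4: "Snore count; OA compliance; Mean disease alleviation; Sleep Quality". The questionnaires sit under a separate list, T0, T2 and T4. The table note says "Mean disease alleviation is a composite measure of the reduction in RDI and OA compliance" and gives no formula.

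Section VII.f.1 defines compliance per night: "This variable is determined by the number of hours that the OA device is worn per hour of sleep per night using Braebon monitors". Section 13.6 adds: "The OA will contain a computer chip that will also record the actual amount of time that the OA is worn each night". For the denominator, the Appliance Acclimation text in VII.g says "Subjects will use diaries to record appliance settings and hours of sleep on each sleep recorded or non-recorded night".

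Section IX.b fixes the time points. T1 is the "first night in week-1 with first OA", T3 is the corresponding first night with the second OA, and T2 and T4 follow four weeks on each device. Under the device-use questions in section 25, "A total of 4 sleep recordings/subject is expected over the 9-week study period". The inclusion criteria ask subjects to be willing "to wear an oral appliance every night for 8 weeks".

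Section VII.i plans to test whether each outcome measure varies across the time points. For non-dichotomous secondary outcomes it names t-tests and Mann-Whitney tests.

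**The concern.** The trial describes itself as comparative effectiveness research and asks which design should be preferred. A device that reduces RDI more but is worn less may do less good overall. Mean disease alleviation is the one listed outcome defined as a combination of efficacy and use, so it is where such a trade-off should appear.

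As listed, compliance and the composite take a value at each of four single nights. Two of those are the first night on a device, when no use of it has accumulated. On all four, the subject is also wearing the home sleep test, and wear may then be better than on an ordinary night. In that case the composite would mostly restate the RDI result, although wear data for every other night had been collected. With no formula or averaging window fixed in advance, the choice would also be open after the data are seen.

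**Working it through.** **1. Nights covered.** Two devices × 2 recordings (first and last night) = 4 recordings, which agrees with the plan's figure. Duration is 4 + 1 + 4 = 9 weeks, which also agrees. Planned wear is 8 weeks × 7 = 56 nights, or 28 per device. Recording nights are 4/56 = 7.1% of these. The remaining 26 nights per device (52/56 = 92.9%) fall outside T1–T4.

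**2. What each time point can measure.**

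| Time point | Wear of that device so far | Can it summarise a treatment period? |
|---|---|---|
| T1 | None before this night | No |
| T2 | Four weeks | Yes, if read as a summary of those weeks |
| T3 | None; the preceding week is CPAP washout | No |
| T4 | Four weeks | Yes, if read as a summary of those weeks |

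Reading T1–4 as read-out times rather than nights rescues T2 and T4, but not T1 or T3.

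**3. Data available.** Hours worn (chip) and hours of sleep (diary) are both recorded every night, so a whole-period value can be computed for each device.

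**4. How much the window could matter (illustration).** Two inputs are missing from the documents and are assumed here. The formula is taken as composite = fractional RDI reduction × (hours worn / hours slept). Wear is taken as 100% on the 2 recording nights per device. On the other 26 nights it is 90% for BT and 50% to 80% for MT.

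Reductions come from the plan's literature figures:
- Table 2, unweighted means recomputed from its pre and post AHI columns: MT 79.6% (six rows), BT 55.2% (seven rows).
- Background text: MT 85%, BT 55.4%. The 85% goes with a stated range of 80–90%, whereas Table 2 also has MT rows of 72% and 64%.

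Whole-period compliance = (2 × 1 + 26 × w)/28, where w is wear on the other nights. This gives 0.536 for w = 0.5, 0.629 for 0.6, 0.814 for 0.8 and 0.907 for 0.9.

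| Window and wear | Table 2 means | Background-text means |
|---|---|---|
| Recording nights only, MT | 0.796 | 0.850 |
| Recording nights only, BT | 0.552 | 0.554 |
| All 28 nights, BT, w = 0.9 | 0.501 | 0.503 |
| All 28 nights, MT, w = 0.8 | 0.648 | 0.692 |
| All 28 nights, MT, w = 0.6 | 0.500 | 0.534 |
| All 28 nights, MT, w = 0.5 | 0.426 | 0.455 |

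**5. Break-even.** MT falls behind BT when wear(MT)/wear(BT) < reduction(BT)/reduction(MT). With Table 2 this is 55.2/79.6 = 0.69; with the background text it is 55.4/85 = 0.65. Above that ratio the ranking does not change. If BT were the device worn less, a whole-period window would widen MT's lead instead.

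**The case against.** The strongest reply is that no sentence restricts compliance to recording nights. VII.f.1 defines it from the chip, chip and diary run every night, and Table 4 calls T1–4 only time points, so T2 and T4 could summarise the preceding four weeks. That is a fair reading of T2 and T4. It does not explain the listing at T1 and T3, and VII.i expects a value at each time point to compare.

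A reader might infer more: that the recording nights are supervised, that wear on them is near complete, and that the composite therefore shows RDI efficacy alone and cannot reveal a device worn less. The documents do not support this. The recordings are made at home with sensors the subject applies. No wear rate is given for any night. The plan itself expects discomfort during acclimation, and removing the device partway through a recorded night would lower compliance. The result also depends on a window and a formula that the plan leaves open.

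Two further points stand. The Epworth scale, SF-36 and symptom measures at T2 and T4 follow four weeks of actual use and partly reflect it. The primary RDI comparison is not affected.

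**Conclusion.** The concern holds in a limited form. The T1–T4 listing is unsuitable for these two variables. At T1 and T3 they cannot describe use over a treatment period, and computed as listed at all four points they would leave out 52 of 56 planned wear nights. How far the composite would then collapse into RDI reduction depends on wear on recording nights, which is unknown. The reversal thresholds of 0.69 and 0.65 rest on an assumed product formula and on literature means. They show that the choice of window can matter, not that a reversal is likely. This is a defect in secondary outcomes that should be corrected before analysis; the data needed are already planned.

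**What to change.** In Table 4 and VII.f.1, replace the T1–4 listing for OA compliance and mean disease alleviation with one value per device:

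- **Compliance:** chip-recorded hours worn divided by diary hours of sleep, across all nights of that device's 4-week period, with non-wear nights counted as zero wear.
- **Mean disease alleviation:** state the formula. One option is that compliance value × percent RDI reduction at the device's end-of-treatment recording (T2 or T4).
- **Comparison:** MT against BT as a paired outcome within subject. This needs saying, because VII.i names the Mann-Whitney test, which is unpaired, for outcomes of this type.

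The cost is a few lines of wording and a little more data handling, with no new visits, measurements or subjects. The drawback is that the denominator rests on self-reported sleep hours, so the plan should also say how nights without a diary entry are handled.

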An increase in oropharyngeal space created by advancement of the mandible occurs in association with inferior movement of the condyles that causes the posterior aspect of the mandible to move away from the maxilla (Christensen's phenomenon). ²¹ The mandible's forward movement away from the maxilla stretches and tightens the lateral walls of the pharynx with the superior constrictor muscle through attachments that includes the tongue. ²¹ Furthermore, this space creating forward movement allows the tongue to rest behind the upper incisors to form an air seal with the soft and hard palate that then facilitates nose breathing. ²¹ An OA's mechanics to move the mandible forward should increase oropharyngeal space with concomitant reduction in the number of apnea and hypopnea events through increased forward torque on the lumen's surrounding musculature.

Midline Traction OA	Bilateral Thrust OA

Provides customized fit for each patient	√	√
Uses separate upper and lower tray pieces	V	√
Advances mandible incrementally	√	√
Advancements performed by a dental sleep specialist	√	√
Single contact point between upper and lower trays	V	
Pulls mandible forward	√	
Two contact points between upper and lower trays		√
Pushes mandible forward		√

V.Hypothesis

 $\rm H_0$: The RDI will not differ when treating adults with moderate to severe (>15 events/hour) OSA between the MT and BT devices. $\rm H_A$: The MT device / intervention will provide greater reduction in the RDI from pretreatment values than the BT device in adults with moderate to severe OSA. Secondarily, proportions of responders to MT device intervention who's RDI is reduced to an acceptable level (< 10 events/hour or >50% change from pre-treatment values) is expected to be higher with MT therapy.

VI.Objectives

The main study objectives are to:

- 1. Quantify the RDI with each OA at the start and end of four weeks of use.
- 2. Compare the RDI of each OA with pre-treatment PSG determined AHI to evaluate the percent reduction.
- 3. Characterize global sleep quality changes associated with the use of the OAs.

We endeavor to model real-world conditions for measuring sleep by utilizing HST and recording in the subject's own sleep environment. Based on previous research, we expect reduction in the RDI with OA use and superior response with the MT OA.

VII.Methods

- a. Study type
 - 1. Single center, cross-over randomized control trial; superiority trial

2. Interventional comparative effectiveness research

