Wilcoxon signed-rank test (matched pairs) for cross-over design for primary variables will be used. For dichotomous secondary variables, data analysis will use logistic regression to adjust for effects of initial severity, age, gender, BMI, ethnicity, SES, phenotypic differences, etc. t-tests and Mann-Whitney tests as needed for non-dichotomous outcomes, depending upon normality. Descriptive statistics (means, standard deviation, medians, interquartile ranges) for each outcome measure will be calculated and bar, boxplot or line graphed for each time point. Repeated measures analysis of variance, parametric or nonparametric one-way analysis of variance, as appropriate, will be used to determine if each of the outcome measures vary across the time points.

1. Handling of missing data

For the primary study endpoint, several methods will be used, including: 1) last observation carried forward, 2) multiple imputations, and 3) imputing a missing value with the group's mean value at that follow-up and frequency.

The set of missing data analyses will serve as a sensitivity analysis for the primary study outcomes. If the data imputation methods for a given endpoint result in disparate statistical inferences, the differences will be investigated and elucidated in the final clinical study report.

j. Right and Safety of Research Participants

The clinical trial will be conducted in accordance with the ethical principles that have their origin in the Declaration of Helsinki and the Belmont Report and that are consistent with Good Clinical Practice (GCP). The laws, regulations and rules of the United States, the state of Texas and the Texas A&M University pertaining to human subjects research will be followed. The rights, safety, and well-being of the trial subjects are the most important considerations and will prevail over the interests of science and society. The available clinical information on the OA devices is adequate to support the proposed clinical trial.

Freely given informed consent will be obtained from every subject prior to clinical trial participation. All patient clinical trial information will be recorded, handled and stored in a way that allows its accurate reporting interpretation and verification. The confidentiality of records that could identify subjects will be protected, respecting the privacy, confidentiality rules and to ensure non-bias reporting requirements.

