13.0 Study Population
13.1 Number of Participants
Approximately how many subjects do you plan to enroll?
38
Provide the rationale for the number of subjects requested (for example, power analysis, sponsor requirements, etc.).
Approximately 38 subjects must complete the study to yield a power of 0.90 with alpha = .05 and an expected Effect Size of at least a 10 point difference in the post-treatment mean RDI scores between MT vs. BT devices. Recruitment will be extended to n=44 to accommodate a 10-20% drop-out rate. The projected numbers are based on Wilcoxon signed-rank test where the expected difference between-treatments (cross-over design) is expected to be at least a 10 point difference in RDI scores. As many as 44 will be enrolled to account for attrition.
Will human subjects be used from the Qatar population?
○ Yes • No
* If Yes, then approval by an IRB in Qatar may also be required.
Will human subjects be used from another international population?
C Yes O No
*If Yes, then approval by an international review board or government may also be required.
Will human subjects be used from a Native American population?
O Yes ⊙ No
*If Yes, then approval by a tribal IRB(s) may also be required.
If Yes for research in Qatar, in another country, or with Native Americans, provide justification for that research being conducted in that particular community.
13.2 Provide the age groups being enrolled into this study (Note the consent documents required for each age group listed in parentheses):
 □ 0-6 (parental consent only, Pediatric Assessment required for Clinical Trials) □ 7-11 (child's assent plus parental permission, Pediatric Assessment required for Clinical Trials) □ 12-17 (consent plus parental permission, Pediatric Assessment required for Clinical Trials) ▼ 18+ (consent only)
Enter the specific age range for study population (if overlap or specific within a category):

13.3 Indicate the gender of participants being enrolled into this study:	
MaleFemale✓ Both male and female	

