By wearing an OA, a subject may experience some discomfort and/or reduced function of the jaw joint (temporomandibular joint) and muscles of the jaw (masticatory muscles) and of the face during and after treatment. Subjects may also experience some reduction in sleep quality due to discomfort while getting used to wearing the OA (acclimation). Other minor risks include temporary irritation of the mouth and oral cavity due to contact with the OA, and excessive salivation or dry mouth from mouth breathing. Repositioning of the lower jaw and tooth movement may also occur, but are typically minor and reversible. Also highly unlikely, a subject could swallow part of an OA should it break.

Describe the approaches you will take to minimize these risks and/or to minimize their impact.

Participants will be carefully monitored for all of these risks (above) by one or more of the study dentists. The subjects will be able to contact a member of the research team 24/7 to address any concerns.

What alternatives are available to subjects outside the research (i.e., what is the standard of care, is the research intervention available without participating)?

No alternative treatment options are available as part of this study. If a prospective subject decides that either oral appliance therapy is not suitable, the alternative is to not enroll in the study and continue CPAP therapy as prescribed. Once enrolled in the study, if the subject decides that either oral appliance therapy is not suitable at any time, he/she may withdraw from the study and continue with CPAP therapy as prescribed.

16.2 What are the potential benefits of this study to individual participants? (This does not include payments, compensation, or incentives.)

The benefits of taking part in this study are:

- 1. Two customized oral appliances are yours to keep upon completion of the study at no cost to you
- 2. Effective devices that do not require electricity to operate, so can be used anywhere
- 3. Reduced apnea and snoring
- 4. Improved sleep quality and continuity
- 5. An effective treatment for obstructive sleep apnea that does not require wearing a face mask
- 6. No air pressure blowing through your nose
- 7. Receiving information on your sleep quality.

The researchers or study coordinator will discuss with you possible options that might be of benefit to you if a sleep issue is discovered.

16.3 What are the potential benefits of this study to the population or society?

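### Comfort is rated only at T4, so a subject who withdraws earlier gives no rating on any appliance worn; a short rating at T2 and at exit would close the gap

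*Combined protocol and SAP*

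**What the plan says.** Table 4 in VII.e puts "OA device preference and perceptions of comfort" in the exploratory column under T4. T4 is the end of the second appliance period wherever it is defined, although Table 4 labels T2 and T3 differently from the abstract and IX.b. This note follows the abstract and IX.b, where T2 is the end of the first appliance period.

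VII.f.3 gives questionnaires at T0, T2 and T4: the Epworth scale, the SF-36 and the Thornton snoring scale. It names no comfort item. VII.g uses the word comfortable, but only to define the jaw position sought in titration.

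On leaving the trial, section 16.1 says that "if the subject decides that either oral appliance therapy is not suitable at any time, he/she may withdraw from the study" and go back to CPAP. VII.h says "Recruitment will be extended to n=44 to accommodate an estimated 20% drop-out rate", and section 13.1 says "Recruitment will be extended to n=44 to accommodate a 10-20% drop-out rate".

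The responder comparison is a secondary hypothesis in V: "Secondarily, proportions of responders to MT device intervention" are expected to be higher. The missing-data paragraph, VII.i.1, opens with "For the primary study endpoint, several methods will be used". It does not say how a subject who stops an appliance counts in the responder proportion.

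**The concern.** The trial aims to say which of two appliance designs should be preferred, and comfort bears on that. Pain or discomfort in the jaw, muscles and mouth is listed among the risks (VII.k), so it is a foreseeable reason to leave. If comfort is asked only at the end of the second period, the results describe those who tolerated both devices well enough to finish. Ratings from those who did not are missing for a reason tied to the rating itself, and no analysis can recover a rating that was never taken.

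Completers have a smaller problem. They recall the first appliance after weeks on another one, whereas the second is rated while in use. The two ratings are therefore not taken under the same conditions.

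**Working it through.** **Inputs.** 44 enrolled and 38 needed (VII.h, 13.1); drop-out 20% (VII.h) or 10-20% (13.1); two 4-week periods with a 1-week washout (VII.g, IX.b).

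**Subjects without a rating, upper limit.**
- The plan's own allowance: 44 - 38 = 6, and 6/44 = 13.6%.
- 10% drop-out: 0.10 × 44 = 4.4, about 4 subjects; 4/44 = 9.1%.
- 20% drop-out: 0.20 × 44 = 8.8, about 9 subjects; 9/44 = 20.5%.

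These figures assume that every drop-out leaves after starting an appliance and before T4. Subjects enrol at the first appointment, before the appliances are made, and are randomised at the second (IX.b, 13.6). If W subjects drop out and W0 of them leave before wearing either device, the ratings lost come from W - W0 subjects. The documents do not give W0, nor the share of drop-out due to discomfort.

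**Recall lag for the first appliance.** 1 week of washout + 4 weeks on the second device = 5 weeks. For the second appliance the lag is 0. This assumes that the T4 item asks about both devices. If it asked only about the second, the first would get no rating at all.

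**What each subject contributes.**

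| Subject | As planned | With ratings at T2, T4 and exit |
|---|---|---|
| Leaves before wearing a device | none | none; nothing to rate |
| Leaves during the first device | none | first device, at exit |
| Leaves in the washout | none | first device, at T2 |
| Leaves during the second device | none | first at T2, second at exit |
| Completes | both at T4, the first 5 weeks late | first at T2, second at T4 |

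A subject who stops wearing a device but stays in the study still reaches T4 and gives a rating, so the gap concerns withdrawal only.

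**Responder proportion (the optional part).** Suppose a proportion r of completers respond on a device, all 44 start it, and W withdraw from it for intolerance. A completers-only analysis gives r. Counting the W as non-responders gives r(44 - W)/44. The difference is rW/44.
- r = 0.7: 0.7 × 4/44 = 6.4 points with W = 4, and 0.7 × 9/44 = 14.3 points with W = 9.
- r = 0.5: 4.5 to 10.2 points. r = 0.8: 7.3 to 16.4 points.

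Here r is assumed, and placing every withdrawal on one device is the extreme case. With no intolerance withdrawals the difference is 0.

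**The case against.** Comfort is exploratory, and early discomfort does not go unobserved. Diaries record appliance settings and hours of sleep (VII.g), a chip records wear time, the study dentists monitor discomfort (13.6, 16.1), and device-related events count as adverse device effects. Case report forms are not among the documents, so an unlisted comfort item may exist. All of this stands and keeps the point small. But wear time and diary hours are not comfort ratings, and no visible text asks for a reason at withdrawal.

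It is also fair to say that 4 to 9 overstates the loss. Drop-out is for any cause, and some of it may come before any device is worn. The range is therefore given only as an upper limit.

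A reader might go further and infer that the missing-data methods would tilt the responder result towards MT. Group-mean imputation uses the "mean value at that follow-up and frequency", the MT post-treatment means in Table 2 are all below 10 (3.2 to 8.4), and the BT means are all above 10 (11.1 to 14). The documents do not support that inference:
- The Table 2 means are AHI values from earlier studies, not this trial's home-test RDI.
- The group in VII.i.1 is not defined and need not be the device.
- VII.i.1 also lists multiple imputation, and it commits to investigating and explaining methods that lead to different inferences.
- A responder may qualify by a reduction above 50%. In all seven BT rows the mean baseline exceeds twice the post-treatment mean (27 v 24 in three rows, 30 v 28, 26.9 v 24.4, 25.6 v 22.2, 26.9 v 24), so a BT subject with an average baseline would also qualify.
- A first-period withdrawal leaves both devices without an end-of-period value, so the effect cannot be counted as missing on one device only.

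Last-observation-carried-forward could in principle reuse a T1 recording ("first night in week-1 with first OA") for someone who then stopped. But the plan does not say that the primary-endpoint methods apply to the responder proportion.

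**Conclusion.** The comfort point holds. As written, a subject who withdraws before T4 gives no comfort rating on any appliance worn, and completers rate the first appliance 5 weeks late. At most about 4 to 9 of 44 subjects (9.1% to 20.5%) are affected, on the plan's own drop-out figures and on the assumption that all of them leave between first wearing a device and T4. The true number is probably lower. The gap is worth closing because those missing are likely to be those most bothered, and the rating cannot be obtained afterwards.

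The unstated handling of stopped devices in the responder proportion is a missing detail, not a demonstrated bias towards either device. The primary matched-pairs RDI test and the sample size are not in question here.

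**What to change.** In VII.e, replace the single T4 comfort item with a short rating of the device just worn at three occasions: T2, when questionnaires are already given; T4; and exit, for anyone who withdraws after starting a device. Record the reason for withdrawal on the same exit form. Keep preference at T4, since it needs experience of both devices.

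Optionally, add to VII.i one sensitivity analysis of the secondary responder proportion, shown beside the completers' result. Withdrawal for intolerance would count as non-response on the device being worn, and a second device never started would stay missing.

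The cost is one extra short item, an exit form and, if adopted, one further analysis. That analysis mixes tolerability with efficacy, so it should remain a sensitivity analysis. Sample size and the primary test do not change.
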